8.5.4 Pharmacokinetic and Safety Endpoints

8.5.4.1 **Primary Endpoints**

- Identification of **DLT** defined as an adverse event occurring during the first treatment cycle, judged to be related to MEN1112 and meeting any of the following criteria:
 - Grade 3 non-haematological toxicity lasting more than 7 days
 - Grade \geq 4 non-haematological toxicity.

Note: Common complications of AML (in particular infections, bleedings, fatigue) will not contribute to DLT assessment.

• Identification of **MTD** defined as one dose level below the Maximum Administered Dose (i.e. one dose level below the one at which ≥ 2 DLTs out of 6 treated patients occur).

8.5.4.2 Secondary Endpoints

- Immunogenicity Evaluation Criteria: Incidence of anti-MEN1112 autoantibodies.
- Clinical Evaluation Criteria:
 - Complete remission (CR) rate at any time point, where CR is defined as: bone marrow blasts <5%, absence of extramedullary disease, absolute neutrophil count >1 x 10⁹/L and platelet count > 100 x 10⁹/L.
 - Composite complete remission (CRc) rate at any time point, defined as the proportion of patients having either CR or CRi (where CRi is defined as: all criteria for CR except residual thrombocytopenia [platelets <100 x 10⁹/L] and/or neutropenia [absolute neutrophil count <1 x 10⁹/L]).
 - Best response rate, defined as the best observed response at any time point between CR, CRi and partial remission ([PR]: all haematologic criteria for CR with bone marrow blasts 5-25% and decrease of pre-treatment bone marrow blast percentage by at least 50%).
 - Duration of CRc: number of days between the date of CR/CRi achievement and the date of the last assessment confirming CR/CRi.
 - Overall Survival (OS), defined as the number of days between the first study drug administration and death from any cause.
 - Correlation of baseline characteristics with clinical activity of MEN1112.

- Incidence, severity, seriousness and treatment related causality of Treatment Emergent Signs and Symptoms (TESSs).
- Frequency of clinically significant abnormalities in physical examination, safety laboratory tests, vital signs and 12-Lead ECG.

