- Blood sampling for PK (pre-infusion)
- Recording of AEs and change in concomitant medications
- TLS risk assessment (see Appendix I: TLS Manual for Investigator)
- TLS prophylaxis (see Appendix I: TLS Manual for Investigator)
- Premedication (see §8.4.2)

Study drug administration

- Study drug administration, given as a 6 h infusion with constant infusion rate
- Blood sampling for safety lab test at following time points after start of infusion: 2h, 4h, 8h, 12h.
- Vital signs every 15 minutes during the first hour of study drug administration and then at the same time points of blood sampling for safety lab test

- 12-lead ECG at the end of infusion
- Blood sampling for PK (at the end of infusion, and 6h after the end of infusion)
- Recording of AEs and change in concomitant medications

Visit 2/Day 2(one day after the completion of Visit 1) and Visit 3/Day 3 (one day after the completion of Visit 2)

Prior to study drug administration

- Physical examination, including vital signs
- PS evaluation
- 12-lead ECG
- Blood samplingfor safety lab test
- Blood sampling for PK (pre-infusion)
- Recording of AEs and change in concomitant medications
- TLS prophylaxis (see *Appendix I: TLS Manual for Investigator*)
- Premedication (see §8.4.2)

Study drug administration

- Study drug administration, given as 6h infusion with constant infusion rate
- Blood sampling for safety lab test at the following time points after start of infusion: 2h, 4h, 8h, 12h
- Vital signs every 15 minutes during the first hour of study drug administration and then at the same time points of
 - blood sampling for safety lab test
- 12-lead ECG at the end of infusion
- Urine collection at the end of infusion (ONLY at Visit 3)
- Blood sampling for PK
 at the end of infusion, 6h after the end of infusion (ONLY at Visit 2), 14h after the end of infusion (ONLY at Visit 3)
- Recording of AEs and change in concomitant medications

Visit 4/Day 4, one day after the completion of the entire first *"ramp-up"*

- Physical examination, including vital signs
- PS evaluation
- Blood sampling for safety lab test
- •
- Blood sampling for PK infusion

24h after the end of last "ramp-up" dosing

Bone marrow aspirate for morphologic assessment,

Recording of AEs and change in concomitant medications

Visit 5-6/Day 5-6, one and two days after Visit 4, respectively

- Blood sampling for PK
 (44h and 68h after the end of last "*ramp-up*" dosing infusion)

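### The CR and CRi definitions leave exact cut-off counts unclassified, do not exclude circulating blasts, and let the Day 4 marrow set a response

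*Combined protocol and SAP*

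**What the plan says.** The response endpoints are in protocol section 8.5.4.2 and are repeated in the synopsis.

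- **CR** requires "bone marrow blasts <5%, absence of extramedullary disease, absolute neutrophil count >1 x" 10⁹/L "and platelet count > 100 x" 10⁹/L. Both count limits are strict.
- **CRi** is worded "where CRi is defined as: all criteria for CR except residual thrombocytopenia" (platelets below 100 × 10⁹/L) "and/or neutropenia [absolute neutrophil count <1 x" 10⁹/L]. Both limits are strict in the other direction, and both counts may be low together.
- **PR** keeps the blood criteria of CR, with marrow blasts of 5–25% and a fall of at least half from the pre-treatment percentage.
- **CR rate, CRc rate and best response** may be met at any assessment. Duration of CRc runs from the date CR or CRi is reached to the last assessment that confirms it.

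The first on-treatment marrow is at "Visit 4/Day 4, one day after the completion of the entire first" ramp-up (section 8.5.1), with safety bloods at the same visit. The next is on Day 22, before the first Cycle 2 infusion. Table 3 in section 8.5.2.6 lists blasts in the white-cell differential. Section 9.2 limits the efficacy population to patients who complete Cycle 1 and have a blood test and marrow after it. Section 9.3.2 makes the efficacy analysis descriptive.

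**The concern.** A response category should place every assessed patient in exactly one class, use the disease evidence collected, and say which assessments may set it. These definitions fall short on each count.

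Strict inequalities on both sides leave the cut-off values unassigned. The blast count in the differential plays no part in CR or CRi, so a patient with leukaemic blasts in the blood can be scored as in remission. With no earliest scoring date, a marrow taken one day after the first split dose can set the patient's best response.

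Section 6.3 reports that no complete or partial response had been documented under the one-shot schedule, so few responders may be seen and each classification would carry weight. The definitions also decide which patients have the conditional marrows at Visits 35 and 37, because those depend on blood results compatible with CR, CRi or PR.

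**Working it through.** The plan gives no sample-size, power or threshold figure for response, so there is none to reproduce. The check applies the definitions literally.

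**(a) Cut-off values.** Take marrow blasts of 2% and no extramedullary disease. Classify combinations of absolute neutrophil count (ANC, rows) and platelets (columns), both × 10⁹/L:

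| ANC | 5 | 50 | 100 | 150 |
|---|---|---|---|---|
| 0 | CRi | CRi | neither | CRi |
| 0.2 | CRi | CRi | neither | CRi |
| 1.0 | neither | neither | neither | neither |
| 1.5 | CRi | CRi | neither | CR |

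The unclassified cells number 4 + 4 − 1 = 7 of 16: one row and one column sharing a cell. The other 9 are 1 CR and 8 CRi. The 7 of 16 reflects the values chosen for the grid and is not a frequency. PR does not catch these patients, because it needs marrow blasts of at least 5%. The 5% marrow cut-off itself has no gap (CR below 5%, PR from 5%).

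With CR set at ANC ≥ 1.0 and platelets ≥ 100, and CRi below either or both, the same grid gives 2 × 2 = 4 CR, 16 − 4 = 12 CRi and none unclassified.

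**(b) Circulating blasts.** Setting section 8.5.4.2 beside Table 3, the blast count is collected but enters neither CR nor CRi. A patient with ANC 1.5, platelets 150 and 2% marrow blasts is CR whatever the peripheral blast count. The only citation of the IWG 2003 criteria is in inclusion criterion 2, where it defines failure of earlier treatment. It therefore does not supply the missing condition for the endpoints.

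**(c) Day 4 marrow.** Suppose a patient has 2% marrow blasts with low counts on Day 4, completes Cycle 1, and has persistent leukaemia in the Day 22 marrow.

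- The post-cycle blood test and marrow place the patient in the efficacy population.
- The Day 4 result meets CRi, and any assessment may count, so the patient enters CRc.
- If no later assessment confirms the remission, duration is Day 4 to Day 4, or 0 days.
- If Day 22 does confirm it, starting the clock on Day 4 adds 22 − 4 = 18 days.

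**Scale.** One patient moves CRc by 1/n.

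- n = 30 (planned expansion): 1/30 = 3.3 points.
- n = 14: 1/14 = 7.1 points. This assumes that the earlier evaluable share, 22/47 = 46.8% (Table 1, one-shot schedule), recurs, since 30 × 22/47 ≈ 14.

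**The case against.** Much can be said on the other side.

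- **The endpoints are secondary, unranked and descriptive.** This stands. It also means that the documents do not support calling CRc the main activity readout of the expansion. CR is reported separately, so the CRi contribution to CRc stays visible.
- **The efficacy population already deals with Day 4.** Partly. A patient whose only on-treatment marrow is Day 4 falls outside it. But section 9.2 governs who is counted, not which marrow sets the response, and the protocol does not expressly tie the CR and CRc rates to that population.
- **A boundary patient is lost only if every otherwise qualifying assessment falls exactly on a cut-off.** This stands, and makes (a) the smallest of the three.
- **The SAP may settle this.** Section 9.5 says that a SAP finalised before database lock will detail the endpoints. It could do so, but the protocol holds the governing definition.

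A reader might also infer that CRi should require recovery of at least one lineage. The protocol expressly allows either or both to be low, which is a coherent reading of incomplete recovery. The target is highly expressed on normal neutrophils and monocytes (section 6.2.2.1.2), so low counts could be a treatment effect in a patient with a real marrow response.

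Nor can the absence of cellularity or sample-quality rules be concluded. Text following the marrow entries is redacted, and section 8.5.1.1 leaves sample collection and handling to separate Laboratory Manuals.

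**Conclusion.** The point holds for the three drafting defects: the unassigned cut-off values, the unused circulating blasts, and the eligibility of the Day 4 marrow. Defects (b) and (c) can overstate CRc; (a) can understate it, probably rarely. Each misclassified patient is worth 3.3 points at n = 30. The frequency of misclassification cannot be computed from the documents, and DLT and MTD are unaffected. The conclusion rests on the visible text, read literally.

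Two stronger conclusions are not supported. It is tempting to say that two false responses would create a signal, because 2/30 = 6.7% exceeds the one-sided 95% upper bound for 0/47, 1 − 0.05^(1/47) = 6.2%. A point estimate set against a bound is not a test, and the exact 95% interval for 2/30 runs from 0.8% to 22.1%. Against the 22 efficacy-evaluable patients the bound is 1 − 0.05^(1/22) = 12.7%, and 6.7% lies below it. Those patients also had a different schedule, and the plan sets no response threshold.

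Nor does a response call by itself give access to further drug. The sponsor undertakes only to consider supply for individual patients achieving at least PR, with iDSMB input and discussion with the investigator and Medical Monitor.

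**What to change.** In section 8.5.4.2, the synopsis and the SAP:

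1. Define CR with ANC ≥ 1.0 and platelets ≥ 100 × 10⁹/L, and CRi with either or both below those values, keeping the existing allowance for both to be low. The revised limits carry into PR, which borrows the blood criteria of CR.
2. Require no circulating blasts in the differential for CR and CRi, and state explicitly whether this also applies to PR.
3. Score responses and start CRc duration from the Day 22 marrow onwards. Report the Day 4 marrow descriptively only.
4. Optionally, tabulate CRi with both counts low as a separate line within CRc.

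The cost is definition wording. Blood counts, differential and marrow are already collected, so no visit or sample is added. The downside is that CRc may be slightly lower and a genuine early response would be dated later.

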	any time point between CR, CRi and partial remission ([PR]:
	all haematological criteria for CR with bone marrow blasts 5-
	25% and decrease of pre-treatment bone marrow blast
	percentage by at least 50%).
•	Duration of CRc: number of days between the date of CR/CRi
	achievement and the date of the last assessment confirming
	CR/CRi.
•	Overall Survival (OS), defined as the number of days between
	the first study drug administration and death from any cause.
-	Correlation of baseline characteristics with clinical activity of
	MEN1112.

Immunogenicity	Incidence of anti-MEN1112 auto-antibodies.
Endpoint Pharmacokinatic	
endpoints	PK parameters will be calculated, as data permit, following each of
	the three doses of the first "ramp-up" administration visit during
	Cycle 1 and following the third "one-shot" administration visit
	during Cycle 2.
	The following PK variables will be assessed following the 1 st and 2 nd
	dose of the first "ramp-up" administration visit during Cycle 1:
	C _{max} , t _{max} , C _{trough} , C _{avg} , AUC _(0-t)
	The following PK variables will be assessed following the 3 rd dose of
	the first "ramp-up" administration visit during Cycle 1:
	C _{max} , t _{max} , C _{trough} , C _{avg} , C _{last} , t _{last} , AUC _(0-t) , AUC _(0-∞) , %AUC _{ex} , k _e , t _{1/2} ,
	CL, V _{ss} , Vd, AUMC _(0-∞) , MRT.
	Total AUC following the first "ramp-up" administration visit during
	Cycle 1 will be calculated as the sum of $AUC_{(0-t)}$ related to each dose.
	The following pharmacokinetic variables will be assessed following
	the 3 rd "one-shot" administration visit during Cycle 2:
	Cmax, tmax, Ctrough, Cavg, Clast, tlast, AUC(0-t), AUC(0-co), %AUCex, ke, t1/2,
	CL, V _{ss} , Vd, AUMC _(0-∞) , MRT, accumulation ratio (Ro).
Safety endpoints	 Incidence, severity, seriousness and treatment related
	causality of Treatment Emergent Signs and Symptoms
	(TESSs).
	 Frequency of clinically significant abnormalities in physical
	examination, safety laboratory tests, vital signs and 12-Lead
	ECG.
Sample size	Due to the nature of the study, no formal sample size calculation is
-	applicable.
	Starting from protocol version 6.1/6.2 up to approximately 6 DLT
	evaluable patients per dose level will be treated with MFN1112
	during the dose escalation phase while up to approximately 30
	patients will be treated in the cohort expansion phase. Considering

that the patients no-DLT evaluable during the dose escalation phase

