- Bone marrow aspirate for morphologic assessment on Visit 35 and Visit 37 only in patients showing peripheral blood labs consistent with CR/CRi/PR
- Recording of AEs and change in concomitant medications.

NOTES:

- To serve the best interest of the patients, for those achieving at least a partial remission, the Sponsor commits to consider providing MEN1112 to allow the prosecution of the infusions at the frequency recommended by the iDSMB on an individual basis and after discussion with the treating Investigator and the Medical Monitor. In this case, premedication and safety assessments will resemble those already described for study drug administration visits, unless differently advised by the iDSMB.
- During Follow-up Period, a time-frame of + 2 days each is allowed at any visit, however the scheduled time of the following visits should be maintained.

END OF STUDY

End of Study Visit (180 days after Visit 1/Day 1)

- Physical examination and vital signs
- PS evaluation
- Blood sampling for safety lab test including pregnancy test (if applicable)
- .

- Bone marrow aspirate for morphologic assessment,
- Recording of AEs and change in concomitant medications

NOTES:

- At the End of Study Visit, a time-frame of + 5 days is allowed.
- All patients shall undergo the End of Study Visit at the scheduled date or at the time of study withdrawal. Unscheduled assessments showing disease progression and leading to patient's withdrawal can replace the End of Study Visit provided that all assessment/procedures scheduled for this visit are completed.
- In case the patient is discontinued from the study within the treatment period, the End of Study Visit bone marrow aspirate is highly recommended to be performed.

GENERAL NOTES:

- For each safety lab test, blood sampling for PK (except for those to be collected at the end of infusion) and for vital signs, a window of +/- 5% of the required time interval is allowed.
- The total dose calculated for the first study drug administration can be applied also for the following ones providing that actual patient's weight is within ±10% of the weight measured prior to the first study drug administration; otherwise, the total dose to be given shall be calculated based on the weight measured at the corresponding visit.

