- Any effort aimed at preserving patient's safety and/or further clarifying an adverse event is recommended, including unscheduled assessments (e.g. additional safety lab sampling, additional safety lab parameters). The anonymized documentation of the above unscheduled assessment shall be then provided to the Sponsor.
- It is strongly recommended not to start the treatment on the day prior to -or onweekends/holidays, unless the treatment is deemed not deferrable by the Investigator in view of the specific patient's clinical situation. In such case, the site shall anyway guarantee the actual availability of site personnel as well as the actual feasibility of ALL study procedures as required by the protocol.

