9.3 STATISTICAL ANALYSIS

9.3.1 Descriptive statistics

All study variables (with the exception of PK variables) will be presented by cohort, dose and overall, by using the appropriate descriptive statistics according to the variable nature, unless otherwise specified:

- Continuous variables: number of non-missing observations, arithmetic mean, standard deviation (SD), minimum, median, maximum.
- Categorical variables: number of non-missing observations and column percentages (N, %).
- Time to event variables: number of non-missing observations, number and percentage of censored observations, 1st quartile, median and its 95% CI, 3rd quartile, Kaplan-Meier survival curves and event rate every 21 days.

The behaviour over time of study variables will be summarised by cohort and overall as follows:

- Continuous variables: descriptive statistics for each time point and for the absolute/percentage differences to baseline.
- Discrete variables: descriptive statistics for each time point and shift tables to baseline.

The Overall Survival (OS) is calculated as:

- In case of all-cause death:
 - OS = date of death date of first study drug administration + 1.
- In case of censored information not for drop-out:
 - OS = date of end of observation period (i.e. study end / end of survival follow-up) date of first study drug administration + 1.
- In case of censored information for drop-out:
 OS = Last date known alive date of first study drug administration + 1.

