9.3.2 Efficacy Analysis

Efficacy analyses will be performed only through descriptive statistics.

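### Duration of CRc stops at the last assessment in remission and has no event or censoring rule, so lost and ongoing remissions score alike

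*Combined protocol and SAP*

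**What the plan says.** The endpoint appears twice, in section 8.5.4.2 ("Duration of CRc: number of days between the date of CR/CRi achievement and the date of the last assessment confirming CR/CRi") and in the synopsis, where the stop date is likewise described by "achievement and the date of the last assessment confirming" remission. Neither place says what ends a remission or who is censored.

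Section 9.3.1 sets a general format: "Time to event variables: number of non-missing observations, number and percentage of censored observations", followed by quartiles, median and Kaplan-Meier curves. Duration of CRc is not named as belonging to that class. The one worked derivation that follows begins "The Overall Survival (OS) is calculated as" and gives three cases: death, censoring at the end of observation, and censoring for drop-out. Section 9.3.2 adds "Efficacy analyses will be performed only through descriptive statistics".

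CR and CRi both require a bone marrow blast count. After Day 4, marrows are scheduled in section 8.5.1 at Day 22, Day 42, Day 65, Day 121 and the End of Study Visit, 180 days after Day 1. The two in follow-up are conditional: "Bone marrow aspirate for morphologic assessment on Visit 35 and Visit 37 only in patients showing peripheral blood labs consistent with CR/CRi/PR". Other dates can arise, since "Unscheduled assessments showing disease progression and leading to patient's withdrawal can replace the End of Study Visit" and the general notes encourage extra work-up of adverse events, "including unscheduled assessments (e.g. additional safety lab sampling, additional safety lab parameters".

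**The concern.** A duration needs an end. Here the end is the last sighting of the patient in remission, and nothing records whether the remission then ended, continued or went unobserved. Kaplan-Meier needs an event indicator, and this definition supplies none. One programmer could code every value as an event and another every value as censored, and both would comply with the text.

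Duration of CRc is a listed measure of clinical activity. If remissions occur, they are likely to be few, and one or two durations may be the whole result. A reader given bare values could not tell a lost remission from a continuing one, or see that a value is a lower bound.

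Other AML treatment, including transplant, is a reason to stop study treatment in section 8.2.3. No analysis rule says whether remission assessed after it still counts.

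**Working it through.** The plan gives no figure for this endpoint, so there is nothing to reproduce. The check reads the definition against the visit schedule and then illustrates the size.

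**1. Marrow gaps.** From Days 4, 22, 42, 65, 121 and 180: 18, 20, 23, 56 and 59 days (the last is 60 if 180 days after Day 1 is read as Day 181).

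**2. Same value, different outcome.** CR on Day 65, confirmed on Day 121, scores 121 − 65 = 56 days if relapse is found at End of Study. It also scores 56 days if the patient is lost to follow-up after Day 121 while in remission. A patient still in remission at Day 180 scores 180 − 65 = 115 days with nothing to show that the remission is ongoing.

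**3. One sighting.** First and last confirming dates coincide, so the value is 0 days (1 day with the +1 used for overall survival).

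**4. Direction.** For one continuous remission, the last confirming date cannot fall after the true end, so the value is at or below the truth. An extra visit that shows relapse leaves the value unchanged; an extra marrow in remission raises it. If CR is seen on Day 22, absent on Day 42 and seen again on Day 121, the wording can give 121 − 22 = 99 days, spanning both remissions and overstating each.

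**5. Illustrative size.** Assumptions: one continuous remission, exponential time to loss counted from detection with S(t) = 2^(−t/m) and true median m, and confirmation only at scheduled marrows. The chance of recording the value at marrow i is S(tᵢ) − S(tᵢ₊₁); for the last marrow it is S(t_last). The recorded median is the first value at which the cumulative chance reaches 0.5.

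| First CR/CRi | True median | Possible values (days) | Chances | Recorded median |
|---|---|---|---|---|
| Day 42 | 60 | 0, 23, 79, 138 | 0.233, 0.365, 0.198, 0.203 | 23 |
| Day 42 | 90 | same | 0.162, 0.293, 0.199, 0.345 | 79 |
| Day 42 | 180 | same | 0.085, 0.178, 0.150, 0.588 | 138 |
| Day 22 | 60 | 0, 20, 43, 99, 158 | 0.206, 0.185, 0.290, 0.157, 0.161 | 43 |
| Day 22 | 90 | same | 0.143, 0.139, 0.252, 0.170, 0.296 | 43 |
| Day 22 | 180 | same | 0.074, 0.078, 0.164, 0.139, 0.544 | 158 |

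For example, Day 42 with m = 60: 0.233 + 0.365 = 0.598, so the median is 23. With m = 180, 59% (Day 42) or 54% (Day 22) are still in remission at Day 180. The true median is then not reached, yet 138 or 158 days would be recorded.

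**6. Sensitivity.** Using Day 181 moves these medians by at most one day. Letting the blood visits labelled Day 85 and Day 149 confirm remission changes two of the six: 23 becomes 43 (Day 42, m = 60) and 43 becomes 63 (Day 22, m = 90).

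**7. Few responders.** For a single responder, the chance of an ongoing remission at Day 180 is the last entry in each row: 16–20%, 30–35% and 54–59% for m = 60, 90 and 180. An upper-end scenario takes the one-sided 95% limit for 0 of 47 treated, 1 − 0.05^(1/47) = 6.2%. Times 60 patients that is 3.7, or about four responders. The chance that at least one of four is ongoing, 1 − (1 − p)⁴, is then 50–60%, 75–82% and 96–97%.

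**The case against.** The strongest reply is that section 8.5.4.2 is endpoint wording, not a derivation. Its overall survival line names no censoring either, and the censoring appears only in section 9.3.1. Kaplan-Meier is already planned for time-to-event variables, and section 9.5 leaves endpoint detail to a SAP not yet final. So a reader should not infer that the sponsor will certainly report uncensored durations; the documents do not say so. That limit stands. But the overall survival definition contains an event, death, to which censoring can be added. The CRc definition contains none, so its stop date has to be replaced, not merely supplemented.

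Second, withdrawal reasons and visit-level results are collected, so lost and ongoing remissions can be separated. This is correct, and is why the remedy is cheap. The present definition does not use that information.

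Third, a reader might infer that every value is an understatement, or that the medians above forecast the trial. Neither is supported. A remission lost and regained can be overstated. The medians rest on exponential loss and marrow-only confirmation, and the definition refers to an assessment rather than a marrow, although the CR criteria favour the marrow reading. Four responders is an upper-limit scenario, and section 6.3 reports no complete or partial response so far.

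**Conclusion.** The concern holds in a bounded form. Followed as written, the definition scores lost and ongoing remissions alike, gives 0 days (or 1) to a remission seen once, and for a single continuous remission returns a value at or below the truth. For a remission lost between marrows, the shortfall is at most the gap to the next marrow, 56 or about 59–60 days late in follow-up; for one still ongoing it is open-ended. With loss and regain the error can run upward.

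These statements follow from the text and the schedule. Only the medians and probabilities depend on the assumed model. Practical impact is modest, because the endpoint is secondary and descriptive and matters only if remissions occur. It is worth correcting before the SAP is finalised.

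**What to change.** Redefine duration of CRc as the time from first CR/CRi to first documented relapse (loss of CR/CRi) or death from any cause, whichever comes first. Censor patients with neither at their last assessment in remission. State how transplant or new AML therapy is handled in the analysis. Name the endpoint as a time-to-event variable under section 9.3.1 and summarise it by Kaplan-Meier with the number censored. List each responder's duration with status (lost or ongoing), last-confirmed date and first-loss date. Say whether the +1 day convention applies.

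The cost is endpoint and SAP wording; section 9.5 has the SAP finalised before database lock, and no visit is added. The downside is that dating loss at the first assessment that documents it can err upward by up to one visit gap. On scheduled marrows alone, the illustration gives Kaplan-Meier medians of 79 days (Day 42 detection) or 99 days (Day 22) for a true 60, and 138 or 99 days for a true 90. For a true 180 the median is correctly not reached. Relapses caught at unscheduled or withdrawal visits would be dated earlier. The listed pair of dates makes the remaining uncertainty visible, so an interval-censored analysis is not needed.
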